5.3.4. Biomarkers

As part of an ongoing effort by Lilly to better understand how to predict which tumors are more likely to respond to LY3009120 treatment, the collection of samples for biomarker research is a mandatory part of this study. Additional details about sampling are summarized in Sections [8.2.4](#) and [8.2.5](#), [Attachment 1](#), [Attachment 4](#), and [Attachment 8](#).

It is possible that biomarker data for patients in the study have already been generated from samples that were collected and analyzed before enrolling in this trial. These may include data generated from genetic analyses. If available, these data may be requested from medical records for use in the research described in Section [5.3.4.3](#).

5.3.4.1. Pharmacodynamic Biomarkers in Part A

In Part A, PD biomarkers will be used to assess target engagement for LY3009120 in tumor tissue, and may include, but not be limited to, phospho-ERK, p27, and Ki67 protein expression in tumors.

Tumor tissue for PD evaluation will be collected via core needle or excisional biopsy pre-treatment (≤ 14 days pre-treatment) and after 4 weeks of treatment (C1 D28 ± 14 days) for patients added to any Part A cohort that will be expanded to determine MTD, and/or for patients added to any cohort expanded to explore a potential Phase 2 dose based on PK, safety, and

possibly early efficacy data. Selection of patients for PD biopsies will be communicated to the sites by the sponsor.

5.3.4.2. Archived Sample Biomarkers for Stratification in Part B

In Part B, patients will be stratified into cohorts based on existing local determination of molecular alterations, or lack thereof, in B-Raf, NRas, or KRas from archived tissue (see Section 6.1.1 for specific alterations).

5.3.4.3. Exploratory Analysis of Predictive Biomarkers

Potential predictive biomarkers of efficacy to LY3009120 will be measured in archived tumor tissue, tumor tissue from core or excisional biopsies, and plasma. Core or excisional biopsies for exploratory biomarker analysis will be performed on patients enrolled in all cohorts in Part B (see Section 6.1.1 Inclusion Criterion [3]) before receiving the first dose of study drug, but this will not delay treatment. Exploratory biomarker analysis may be performed on preexisting archival samples from patients in Part A and Part B. The predictive biomarkers to be studied may include, but not limited to, somatic alterations in cancer-related genes such as B-Raf, NRas, KRas, and cKIT. In plasma, analysis of biomarkers may include, but not limited to, potential nucleic acid predictive profiles to better understand the disease process and to develop predictive biomarkers.

5.4. Rationale for Selection of Dose

A dose range from 100 to 1400 mg/day (50 mg BID to 700 mg BID orally) of LY3009120 administered is planned based on nonclinical toxicology and PK/PD modeling of nonclinical tumor growth and phospho-ERK (pERK) data. Twice daily dosing is recommended due to the predicted human elimination half-life of 6 hours and to maintain maximum pERK inhibition, given the observed direct relationship of PK with pERK inhibition in preclinical species.

A daily dose of 100 mg is predicted to be safe in patients based on nonclinical toxicology data. The planned clinical starting human dose of 100 mg/day (equivalent to 61.7 mg/m²) is 7-fold and 13.0-fold lower than the MTD/HNSTD dose level of 450 and 800 mg/m² in rats and dogs, respectively. Table JBDA 5.1 shows dose multiples based on body surface area and exposure multiples based on predicted human AUC for the proposed clinical doses.

Tumor growth data from experiments with the A375 xenograft models in rats showed that 5 mg/kg BID dosing of LY3009120 was efficacious. The observed total drug exposure in plasma at this dose level was $AUC_{0-12h} = 2200 \text{ ng}\cdot\text{h/mL}$, with a range of 1550 to 3200 ng·h/mL. Due to interspecies differences of 1.6 fold in protein binding, the total AUC_{0-12h} in human will need to be 3520 (2480 to 5120) ng·h/mL to achieve the same unbound concentration in human as that observed in the rat efficacy model. Doses needed to achieve this in clinical conditions were predicted to be approximately 500 mg BID. At this dose, predicted peak pERK inhibition based on PK/PD modeling is predicted to be around 70%.

6. Investigational Plan

6.1. Study Population

Individuals who do not meet the criteria for participation in this study (screen failure) may be re-screened. Individuals may be re-screened up to 1 time. The interval between re-screenings should be at least 4 weeks (28 days). Each time re-screening is performed, the individual must sign a new ICF and will be assigned a new identification number.

B-Raf mutational status should be documented for all patients enrolled in the study. Results from previous testing or retesting of available archived tissue are acceptable. Patients who do not have results from previous testing or adequate archived tissue available for B-Raf mutation retesting will have to undergo a biopsy prior to study drug administration (although results of B-Raf mutational status are not required before study drug administration).

Prospective approval of protocol deviations to recruitment and enrollment criteria, also known as protocol waivers or exemptions, are not permitted.

6.1.1. Inclusion Criteria

Patients may be included in the study if they meet **all** of the following criteria during screening prior to first dose of study drug.

- [1] Part A: Have histological or cytological diagnosis of cancer that is advanced and/or metastatic. The patient must be, in the judgment of the investigator, an appropriate candidate for experimental therapy after available standard therapies have failed to provide clinical benefit for their disease or have a disease for which no proven effective therapy exists.

Part B: All patients must have histological or cytological evidence of cancer that is advanced and/or metastatic and have one of the alterations in the Ras/Raf pathway assessed by previous local somatic mutation testing (from archived tissue) listed below. Patients must have failed or be ineligible for available therapies for their disease, or have a disease for which no proven effective therapy exists.

- Confirmation Cohort A: Advanced unresectable/metastatic melanoma carrying a B-Raf V600X (where X represents any amino acid) mutation that has relapsed after treatment with B-Raf inhibitors, MEK inhibitors, or the combination of B-Raf/MEK inhibitors.
- Confirmation Cohort B: Advanced unresectable/metastatic melanoma carrying a NRas mutation.
- Confirmation Cohort C: Advanced unresectable/metastatic NSCLC carrying a KRas or B-Raf mutation.

- [2] Part A: Have the presence of measurable and/or nonmeasurable disease as defined by the Response Evaluation Criteria in Solid Tumors (RECIST 1.1) (Eisenhauer et al. 2009). Tumor lesions located in a previously irradiated area can be considered measurable only if they are new or if have shown unequivocal progression.
- Part B: Have the presence of measurable disease as defined by the Response Evaluation Criteria in Solid Tumors (RECIST 1.1) (Eisenhauer et al. 2009).
- [3] Part A and Part B: Have a tumor that is safely amenable to core needle or excisional biopsies
- [4] Are ≥ 18 years of age.
- [5] Have given written informed consent prior to any study-specific procedures.
- [6] Have adequate organ function, including:
- Hematologic: Absolute neutrophil count (ANC) $\geq 1.5 \times 10^9/L$ (without use of CSFs within the preceding 14 days), platelets $\geq 100 \times 10^9/L$ (without platelet transfusion in the preceding 14 days), and hemoglobin ≥ 8 g/dL (without transfusion in the preceding 14 days).
 - Hepatic: Bilirubin ≤ 1.5 times upper limits of normal (ULN) (If the total bilirubin is >1.5 times ULN, and a subsequent direct bilirubin test is normal, the investigator and the Lilly Clinical Research Physician will determine patient eligibility.), alanine aminotransferase (ALT), and aspartate aminotransferase (AST) ≤ 2.5 times ULN. If the liver has tumor involvement, AST and ALT equaling ≤ 5 times ULN are acceptable
 - Renal: Serum creatinine ≤ 1.5 times ULN and calculated creatinine clearance ≥ 60 mL/min/1.73m² (Creatinine Clearance Formula, Protocol [Attachment 7](#))
- [7] Have a performance status of 0 or 1 on the Eastern Cooperative Oncology Group (ECOG) scale (refer to [Attachment 6](#)).
- [8] Have discontinued all previous therapies for cancer (including chemotherapy, immunotherapy, corticosteroids, and radiotherapy) and recovered from the acute effects of therapy (treatment related toxicity resolved to Grade 1 or less) for at least 5 half-lives or a minimum of 4 weeks, (at least 42 days for mitomycin-C or nitrosoureas, 14 days for radiotherapy), prior to initiating study treatment.
- At the discretion of the investigator, hormone-sensitive prostate cancer patients who are stable on gonadotropin-releasing hormone (GnRH) agonist therapy and breast cancer patients who are stable on anti-estrogen therapy (for example, an aromatase inhibitor) may have that treatment continued while they are enrolled in Study JBDA.
- [9] Are reliable and willing to make themselves available for the duration of the study and are willing to follow study procedures.

- [10] Males and females with reproductive potential must agree to use medically approved contraceptive precautions during the trial and for 6 months following the last dose of study drug.
- [11] Females with child bearing potential must have a negative serum pregnancy test ≤ 3 days before the first dose of study drug.
- [12] Have an estimated life expectancy, in the judgment of the investigator, of at least 12 weeks.
- [13] Are able to swallow capsules.

6.1.2. Exclusion Criteria

Potential study patients may not be included in the study if any of the following apply during screening.

- [14] Have received treatment within 5 half-lives or a minimum of 28 days of the initial dose of study drug with an investigational product or non-approved use of a drug or device (other than the study drug/device used in this study) for non-cancer indications or are concurrently enrolled in any other type of medical research judged not to be scientifically or medically compatible with this study.
- [15] Have serious preexisting medical conditions that in the opinion of the investigator would preclude participation in the study.
- [16] Have active central nervous system (CNS) or leptomeningeal metastasis (brain metastasis) at the time of study entry. Patients with a history of a CNS metastasis previously treated with curative intent (eg, stereotactic radiation or surgery) that have not progressed on follow-up imaging, have been asymptomatic for at least 28 days and are not receiving corticosteroids and/or anticonvulsants, are eligible. Patients with signs or symptoms of neurological compromise should have appropriate radiographic imaging performed before study entry to rule out brain metastasis.
- [17] Have current hematologic malignancies.
- [18] Have an active fungal, bacterial, and/or known viral infection including human immunodeficiency virus (HIV) or viral (A, B, or C) hepatitis (screening is not required).
- [19] Part A: Have a second primary malignancy that in the judgment of the Investigator and of the sponsor may affect the interpretation of results.
Part B: Have a second primary malignancy treated within the previous 5 years
 - Exemptions will be permitted on a case-by-case basis after prior approval by the lead Lilly physician or designate, if in the judgment of the investigator the patient's risk of recurrence and death is very low.
 - **Exceptions:** The following will be allowed

- Adequately treated nonmelanoma skin cancer or in situ carcinoma of any origin regardless of the time of treatment

[20] Have QTcF (Fridericia corrected) interval of >470 msec on screening electrocardiogram (ECG).

[21] Have significant clinical/instrumental findings of:

[figure not shown]
- Advanced dry age-related macular degeneration (AMD) or any wet-AMD.
- Central or branch retinal artery or venous occlusion with significant vision loss
- Moderate or worse non-proliferative diabetic retinopathy that is undergoing active treatment
- Active non-drug related uveitis, or evidence of any drug-related active ocular inflammation, including but not limited to, anterior chamber cell, vitreous cell, and active keratic precipitates
- macular atrophy due to other cause or retinal thinning on Optical Coherence Tomography (OCT) examination.
- Night vision impairment that is of recent onset (in the last year), sudden and progressive
- Other retinal diseases that cause current visual impairment or would likely cause visual impairment over the time period of the study, as assessed by an ophthalmologist

6.2. Summary of Study Design

Study JBDA is a multicenter, nonrandomized, open label, dose-escalation Phase 1 study of oral LY3009120 in patients with advanced or metastatic cancer. Patients will receive LY3009120 administered orally every 12 hours (BID) daily, in a 28-day cycle. LY3009120 will be administered as a flat dose. Study JBDA will consist of a dose-escalation phase in patients with advanced/metastatic cancer (Part A) followed by a dose-confirmation phase in advanced or metastatic melanoma carrying B-Raf or NRas mutations and NSCLC carrying KRas or B-Raf mutation (Part B).

The dose-escalation phase (Part A) ([Figure JBDA 6.1](#)), described in Section [7.2.2](#), will be guided primarily by safety assessments from Days 1 through 28 of Cycle 1 for patients in all cohorts. Dose escalation will occur until the maximum tolerated dose (MTD, defined in Section [7.2.2.1](#)) is determined. Patients will be enrolled in cohorts starting with the first dose level at 50 mg BID; dose levels of LY3009120 ranging from 50 to 700 mg BID may be evaluated. [Table JBDA 7.1](#) outlines the proposed dose-escalation scheme. The maximum dose increase that will be allowed is 100%. If the MTD has not yet been reached at the highest prespecified dose level, then additional dose levels may be investigated based on both safety and the available PK data. However, dose increments beyond 700 mg BID will never exceed a maximum increment of 33%. Patients in all cohorts will not be enrolled in the next cohort until safety from the previous cohort has been assessed. In Part A, the sample size is estimated to be approximately 30 to 35 patients depending on the relationship between exposure and toxicity as well as the relationship between exposure and pharmacodynamic effects.

After the last patient on Part A has completed Cycle 1 and the recommended dose for the dose-confirmation phase is determined, Part B will begin following an interim review of the data, as outlined in Section 10.9. The dose-confirmation phase will be opened in 3 cohorts of approximately 15 patients each, treated at a dose no greater than the MTD.

- Cohort A: Advanced unresectable/metastatic melanoma carrying a B-Raf V600X (where X represents any amino acid) mutation that has relapsed after treatment with B-Raf inhibitors, MEK inhibitors, or the combination of B-Raf/MEK inhibitors
- Cohort B: Advanced unresectable/metastatic melanoma carrying a NRas mutation
- Cohort C: Advanced unresectable/metastatic NSCLC carrying a KRas or B-Raf mutation

Figure JBDA 6.1. Study Design

The total sample size for Parts A and B is estimated to be approximately 80 patients. A total of approximately 45 patients has been selected in the dose-confirmation phase to ensure an adequate sample size for assessing the safety, PK, and preliminary efficacy signals. The sample size of approximately 15 for each confirmation cohort provides a reasonable power to explore preliminary signals of efficacy. If we assume that a true overall response (complete response [CR] + partial response [PR]) rate less than 10% indicates inadequate anti-tumor activity, then at a one-sided type 1 error rate of 5%, the sample size of 15 will provide 73% power if the true overall response rate is 30% or higher.

pERK will be investigated as one of the candidate biomarkers. We are looking for 50% or higher pERK inhibition in treated patients. If we assume less than 10% patients reach 50% or higher inhibition, then 100% biopsies in 15 patients will provide 73% power if more than 30% patients reach 50% or higher inhibition, at a one-sided type 1 error rate of 5%.

The planned duration of treatment is 2 cycles. Patients may, however, remain on study for additional cycles if they are receiving clinical benefit (stable disease, partial response [PR], or complete response [CR]) until they fulfill one of the criteria for study discontinuation (Section 6.3). Refer to [Attachment 1](#) for the Study Schedule.

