5.4. General Considerations

Statistical analysis of this study will be the responsibility of Eli Lilly and Company. The analyses for this study will be descriptive, except for possible exploratory analysis as deemed appropriate. Data analyses will be provided by dose groups and for all study patients combined wherever appropriate. For continuous variables, summary statistics will include number of patients, mean, median, standard deviation, minimum, and maximum. Categorical endpoints will be summarized using number of patients, frequency, and percentages. Missing data will not be imputed.

The interpretation of the study results will be the responsibility of the investigator with the Lilly CRP or CRS, pharmacokineticist, and statistician. The CRP or CRS and statistician will also be responsible for the appropriate conduct of an internal review for both the final study report and any study-related material to be authorized by Lilly for publication.

Exploratory analyses of the data not described below will be conducted as deemed appropriate.

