5.7. Efficacy Analyses

The study was not designed to make an efficacy assessment. However, any tumor response data will be tabulated according to study part and patient cohort. A listing of best overall response will be provided by part and cohort. A summary of best overall response will be summarized by dose (Part A) and overall by study part. The percentage of patients with a confirmed response, defined as a complete response (CR) or partial response (PR), will be provided along with a 90% exact confidence interval for the response percentage. The objective response rate is defined as:

$(\# \text{ patients with confirmed CR or PR}) / (\# \text{ patients dosed with study drug})$

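### The stated 73% power at one-sided 5% with 15 patients is not attainable: the rule it implies (4 or more of 15) has exact power 70.3% at type 1 error 5.6%

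*Protocol*

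**What the plan says.** Part B has three confirmation cohorts of about 15 patients each. Protocol 6.2 justifies that number as follows: "The sample size of approximately 15 for each confirmation cohort provides a reasonable power to explore preliminary signals of efficacy". The figures behind this are a null in which a response "rate less than 10% indicates inadequate anti-tumor activity", an alternative "if the true overall response rate is 30% or higher", and the statement that "at a one-sided type 1 error rate of 5%, the sample size of 15 will provide 73% power". SAP 5.3.1 repeats the response statement.

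Protocol 6.2 then applies the same numbers to the share of patients with at least 50% pERK inhibition, again 10% against 30% at one-sided 5%: "then 100% biopsies in 15 patients will provide 73% power if more than 30% patients reach 50% or higher inhibition".

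None of the three sentences names the test, the formula or the number of responders that would count as a signal. On the analysis side, SAP 5.4 says "The analyses for this study will be descriptive, except for possible exploratory analysis as deemed appropriate". SAP 5.7 plans that the confirmed response percentage "will be provided along with a 90% exact confidence interval for the response percentage".

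**The concern.** With 15 patients the number of responders is a whole number, so only a few combinations of type 1 error and power exist. Under the null the expected count is 15 × 0.10 = 1.5, which is too few for a large-sample formula to be trusted. A pair such as 73% power at 5% therefore needs checking against the exact binomial distribution.

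If the pair is not attainable, the reader cannot tell which responder count the figure refers to, and neighbouring counts behave very differently. The figure supports the claim of reasonable power per cohort, and SAP 5.3.4 allows efficacy data to be reviewed cohort by cohort.

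**Working it through.** **Inputs** (Protocol 6.2, SAP 5.3.1): n = 15, p0 = 0.10, p1 = 0.30, one-sided α = 0.05, stated power 73%. Type 1 error is evaluated at p0 and power at p1, the boundaries of the stated ranges.

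**1. Reproducing the 73%.** The method is not stated, so candidate formulas were tried. The one-sample proportion z-test without continuity correction uses the null variance for the critical value and the alternative variance for power:

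Power = Φ{[(p1 − p0) − 1.645 √(p0(1 − p0)/n)] / √(p1(1 − p1)/n)}

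= Φ{[0.20 − 1.645 √(0.09/15)] / √(0.21/15)} = Φ(0.0726/0.1183) = 0.730.

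This matches. Other one-sided 5% versions do not:

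- with continuity correction: 63.0%
- arcsine: 63.8%
- alternative variance only: 51.8%
- null variance only: 82.6%

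**2. The rule this implies.** Critical count = 15 × 0.10 + 1.645 √(15 × 0.09) = 1.5 + 1.91 = 3.41. The null would be rejected at 4 or more responders of 15.

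**3. Exact binomial probabilities, n = 15.**

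| Rule | P(rule met) at 10% (type 1 error) | P(rule met) at 30% (power) |
|---|---|---|
| ≥3/15 | 18.4% | 87.3% |
| ≥4/15 | 5.56% | 70.3% |
| ≥5/15 | 1.27% | 48.5% |

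No cut-off gives 73% power, and the largest power with type 1 error within 5% is 48.5%.

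**4. Could any test reach 73% at 5%?** The most powerful test of exact size 5% rejects at 5 or more, and at exactly 4 with probability (0.05 − 0.0127)/(0.0556 − 0.0127) = 0.870. Its power is 0.4845 + 0.870 × (0.7031 − 0.4845) = 0.675. That is an upper bound for every test at this level, so 73% at 5% is out of reach whatever formula produced it.

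**5. The SAP's planned interval.** The lower limit of an exact two-sided 90% interval corresponds to a one-sided 5% test. At 4/15 it is 9.7%, which does not exclude 10%. At 5/15 it is 14.2%, which does. Read through the planned interval, the chance of excluding 10% when the true rate is 30% is therefore 48.5%.

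**6. Sensitivity to cohort size.** The cohorts are only approximately 15. The rule ≥4/14 has type 1 error 4.4% and power 64.5%; ≥4/16 has 6.8% and 75.4%. Neither gives 73% at 5%.

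The same probabilities apply to pERK, with n read as the number of patients with evaluable biopsy pairs.

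**The case against.** The 73% is not a slip of calculation. It follows from the stated inputs by a standard formula, and the plan does not say that an exact test was meant. On the rule the formula implies, the difference is 2.7 points of power and 0.6 points of type 1 error, and 70% still supports a modest claim of reasonable power for exploring signals. Moving from 14 to 16 patients changes power by more than that. The 48.5% arises only if a strict 5% test is imposed, and the plan contains no such test. The primary objective is a Phase 2 dose, response is documented descriptively, pERK is exploratory, and cohort size is also justified by safety and PK.

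Most of this stands, and it limits the consequence. The normal approximation is an inference, although it was the only one-sided 5% version tried that gave 73%. The large step between 4 and 5 responders is a property of 15 patients that no rewording removes. What does not stand is the figure itself: the sentences state an error rate and a power that cannot hold together, and the bound in step 4 shows this without any assumption about the method.

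**Conclusion.** The three power sentences are wrong as written and should be corrected. For the implied rule of 4 or more of 15, power is 70.3% rather than 73%, and type 1 error is 5.6% rather than 5%. If 5% is held strictly with a whole-number rule, power is 48.5%, which is 24.5 points below the stated figure. A reader cannot tell which applies, and the two rules differ by about 22 points of power (70.3% − 48.5%).

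This rests on 15 independent patients per cohort with true rates of exactly 10% and 30%. For pERK it also assumes that all 15 patients yield evaluable pairs. No primary analysis, patient-level decision or enrolment target depends on the figure.

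**What to change.** In Protocol 6.2 and SAP 5.3.1, replace the response power sentence with wording such as:

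> As a benchmark for a descriptive analysis, 4 or more responders among 15 patients has probability 5.6% if the true response rate is 10% and 70% if it is 30%; for 5 or more of 15 these probabilities are 1.3% and 48%. The exact 90% confidence interval has lower limit 9.7% at 4/15 and 14.2% at 5/15.

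Replace the pERK sentence in Protocol 6.2 with the same probabilities for 15 evaluable biopsy pairs, leaving out the confidence interval remark, since that interval is planned for response only. Neither statement should be presented as an efficacy decision rule.

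An optional clarification: SAP 5.7 already tabulates response data by part and cohort and says "A listing of best overall response will be provided by part and cohort", but it does not say how the response rate and its interval are grouped. One line stating that both are also given for each of cohorts A, B and C would align the analysis with the per-cohort justification.

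The cost is three reworded sentences, one optional line and a less favourable stated figure.

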8.2.4.1. Tissue Collection for Pharmacodynamic Studies

Part A: **Mandatory** tumor biopsies should be collected prior to treatment (following determination of eligibility [≤ 14 days of C1 D1]) and after 4 weeks of treatment (C1 D28 \pm 14 days) for patients added to any cohort that will be expanded to determine MTD and/or for patients added to any cohort expanded to explore potential for Phase 2 dosing on the basis of PK data. Biopsy samples taken within 6 months prior to enrollment will also be permitted as long as patients have not received any recent therapies for the disease prior to starting LY3009120. Sponsor will need to review and approve the timing of in-treatment biopsies performed outside of the allowed 14-day window.

Part B: **Mandatory** tumor biopsies should be collected before treatment (following determination of eligibility [≤ 14 days of C1 D1]) and after 2 weeks of treatment (C1 D15 \pm 5 days). Biopsy samples taken within 6 months before enrollment will also be permitted as long as patients have not received any recent therapies for the disease prior to starting LY3009120.

Tumor tissue biopsies taken either by core needle or excisional biopsy are acceptable provided adequate slides can be obtained. Cytologic samples and fine-needle aspiration specimens are not acceptable. Pathology notes accompanying the archived diagnostic tissue may also be requested.

Details for the handling and shipping of tumor biopsy samples will be provided in a separate document. Instructions and supplies required for the collection, processing, and shipment of the patients' samples will be provided by the sponsor.

The tumor tissue samples will be coded with the patient number and stored for up to a maximum of 15 years after the last patient visit for the study at a facility selected by the sponsor.

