																If applicable to tumor type of the patient (± 3 days while on treatment)

Relative Day Within a Cycle	Cycle 1						Cycle 2					Cycle 3-n		Follow-Up		Comments
	1	2	8	15	22	28	1	8	15	22	28	1	28	Visit 801	Visits 802, 803, and 804 (Long-term Follow-up)	
Pharmacogenetic blood sample, stored (mandatory)				X												
Study Tumor Biopsy (Part A, designated expansion cohorts)						X										± 14 days
Exploratory blood plasma sample						X										

Abbreviations: BP = blood pressure; CTCAE = Common Terminology Criteria for Adverse Events; ECG = electrocardiogram; ECOG = Eastern Cooperative Oncology Group; PK = pharmacokinetic; PD = pharmacodynamic; PR = pulse rate; RR= respiration rate.

Part B: Baseline Assessments

Relative Day Prior to Day 1 of Cycle 1	≤28	≤14	≤3	Comments
Informed Consent				Informed Consent Form signed (prior to performance of any protocol-specific tests/procedures)
Chest X-ray	X			May be omitted in patients having a chest CT scan for their radiological tumor assessment
Radiological Tumor Assessment	X			
Medical History		X		Including any alcohol/tobacco habits
Physical Exam		X		
Vital Signs		X		Including temperature, blood pressure, pulse rate, respiration rate
ECOG Performance Status		X		
ECG		X		Central collection and storage
Hematology (local)		X		
aPTT, PT, PT/INR (local)		X		
Serum Chemistry		X		
Urinalysis (local)		X		
Tumor Measurement (Palpable or Visible)		X		
CTCAE v 4.0 Grading (Preexisting conditions)		X		To be reported only after study eligibility is confirmed.
Concomitant Meds		X		
Exploratory blood plasma sample		X		EDTA tube collection after eligibility confirmed
Study Tumor Biopsy (Part B, all cohorts)		X		Biopsy should be taken only after study eligibility is confirmed (mandatory).
Pregnancy Test (local)			X	Negative results required prior to Cycle 1, Day 1. Only to be performed on women of childbearing potential.
Eye Safety Assessments	X			
Dermatological Evaluation		X		

Abbreviations: aPTT = activated partial thromboplastin time; CT = computed tomography; CTCAE = Common Terminology Criteria for Adverse Events; ECG = electrocardiogram; ECOG = Eastern Cooperative Oncology Group; Meds = medications; PD = pharmacodynamic; PT/INR = prothrombin time/international normalized ratio.

Part B: During and Poststudy Assessments

Relative Day Within a Cycle	Cycle 1					Cycle 2					Cycle 3-n		Follow-Up		Comments
	1	8	15	22	28	1	8	15	22	28	1	28	Visit 801	Visits 802, 803, and 804 (Long-term Follow-up)	

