5.10. Pharmacodynamic Analyses

Pharmacodynamic data from all patients undergoing PD assessments will be analyzed.

Biomarker data from all patients undergoing biomarker assessments will be analyzed by appropriate statistical methods. These data may include, but are not limited to IHC, genetic mutations that are hypothesized to be related to safety, efficacy, drug disposition or pathways associated with the mechanism of action of LY3009120.

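### The only powered pERK criterion (50% or more inhibition, 15 patients) does not reach its stated 73% power in an exact 5% test, and no paired continuous pERK summary is specified for the Part B biopsies

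*Protocol*

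**What the plan says.** Protocol 6.2 sets the aim: "We are looking for 50% or higher pERK inhibition in treated patients". The null is "If we assume less than 10% patients reach 50% or higher inhibition", and the result is "then 100% biopsies in 15 patients will provide 73% power if more than 30% patients reach 50% or higher inhibition", at a one-sided 5% error rate. The text does not say which 15 patients these are. The paragraph before it sizes each confirmation cohort at about 15, using the same 10%, 30% and 73% for tumour response.

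Protocol 8.2.4.1 makes two biopsies mandatory in Part B, one before treatment and one at Cycle 1 Day 15 (within 5 days): "tumor biopsies should be collected before treatment (following determination of eligibility". The Part B baseline schedule in Attachment 1 lists "Study Tumor Biopsy (Part B, all cohorts". With three cohorts of about 15, that is about 45 planned pairs. Protocol 5.3.4.3 says that the baseline biopsy is taken "before receiving the first dose of study drug, but this will not delay treatment".

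On analysis, SAP 5.10 says "Biomarker data from all patients undergoing biomarker assessments will be analyzed by appropriate statistical methods", and that PD data from everyone with PD assessments will be analysed. SAP 5.2 sets the PD population as dosed patients with PD assessments. Protocol 10.7 and SAP 5.11 name phospho-ERK in an exposure-effect analysis that may be done if the data permit. SAP 5.4 gives generic summary statistics for continuous variables. The SAP's sample-size section (5.3.1) does not mention pERK.

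**The concern.** The one pERK statement that carries a threshold, hypotheses and a power promises more than the design delivers. It leaves no room for an unusable pair. It also records only whether each patient passed 50%, so it cannot say how much inhibition was achieved.

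The wider PD text leaves five things open: the pERK scale, how the two biopsies of a patient are combined, which patients are pooled, what happens to an unpaired sample, and which summary is the main one. Patients undergo two mandatory biopsies for this information. If the method is chosen after the values are seen, the target-engagement result is harder to interpret, and a reader who relies on the 73% will misjudge what a negative count means.

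**Working it through.** **Inputs (Protocol 6.2).** p0 = 0.10, p1 = 0.30, n = 15, one-sided 5%, no lost biopsies. The documents give no biopsy-loss rate and no standard deviation for pERK.

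**Reproducing the 73%.** Normal approximation, with the null variance in the critical value and the alternative variance in the power:

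Power = Phi{[p1 - p0 - 1.645 x sqrt(p0(1 - p0)/n)] / sqrt(p1(1 - p1)/n)}

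- sqrt(0.09/15) = 0.0775, and 1.645 x 0.0775 = 0.1274
- sqrt(0.21/15) = 0.1183
- (0.20 - 0.1274)/0.1183 = 0.613, so power = 73.0%

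**Exact binomial.** Error = P(X >= r | n, 0.10); power = P(X >= r | n, 0.30).

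| Pairs | Rule | Error | Power |
|---|---|---|---|
| 15 | >= 5 | 1.3% | 48.5% |
| 15 | >= 4 | 5.6% | 70.3% |
| 14 | >= 4 | 4.4% | 64.5% |
| 13 | >= 4 | 3.4% | 57.9% |
| 12 | >= 4 | 2.6% | 50.7% |
| 10 | >= 4 | 1.3% | 35.0% |
| 36 | >= 8 | 2.4% | 88.8% |
| 45 | >= 9 | 3.2% | 95.3% |

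With 15 patients no cut-off gives 73% at 5%. Even a test randomised between the two rules to spend exactly 5% has power 48.5% + [(5.00 - 1.27)/(5.56 - 1.27)] x (70.3% - 48.5%) = about 67%.

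**Lost pairs.** By the Protocol's own formula, power is 69.0% at 13 pairs, 66.8% at 12 and 61.9% at 10. The exact figures for valid 5% rules do not fall steadily. They are higher at 14, 13 and 12 pairs than at 15, because the permitted cut-off drops from 5 to 4.

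**Precision of the count.** The exact 90% interval is 14% to 58% for 5 of 15, and 20% to 44% for 14 of 45.

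**What a continuous analysis could add (assumption needed).** Suppose inhibition is normal on a suitable scale, such as the log ratio. Shares of 10% and 30% beyond the cut then differ by 1.2816 - 0.5244 = 0.757 SD. Testing the share beyond the cut with unknown SD takes the critical value as the 95th percentile of a noncentral t with n - 1 degrees of freedom and noncentrality -1.2816 x sqrt(n). Power comes from noncentrality -0.5244 x sqrt(n), and is 81.1% at n = 15. This is a test of the proportion, not the power of a geometric mean.

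**The case against.** The strongest reply is that the 15-patient sentence is a sample-size remark and not an analysis plan. Analyses are descriptive (Protocol 10.1, SAP 5.4), neither analysis section contains a binomial pERK test, and 15 is most naturally the cohort size. Reading each cohort separately is defensible, because the cohorts differ in tumour and mutation. The biopsies are also well protected: both are mandatory, inclusion criterion 3 requires a tumour that can safely be biopsied, and a baseline sample from the previous 6 months is accepted under conditions. All of this stands. It limits the point, but it does not make the 73% attainable or supply a paired estimate.

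Two stronger readings are tempting, and the documents do not support them.

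- A reader might infer that the yes/no count is the only pERK analysis and that most of the information is thrown away. Protocol 10.6 and SAP 5.2 and 5.10 cover all patients with PD assessments, phospho-ERK is named for a possible exposure analysis, and nothing says that the continuous values or the other 30 or so pairs are dropped.
- A reader might infer that a few lost pairs turn the test into a coin toss. Setting 70.3% at 15 against 50.7% at 12 compares a rule with 5.6% error to one with 2.6%. Among valid 5% rules, losing one to three pairs does not lower power below the 48.5% at 15. The low power comes from the approximation and the discreteness of the count.

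**Conclusion.** The point holds as a specification gap with one incorrect figure. The stated 73% is not attained at one-sided 5%: exact power is 48.5%, or 70.3% if an error of 5.6% is accepted. This needs no assumption beyond the Protocol's own hypotheses. Using all Part B pairs with the same criterion gives 95.3% at 45. The figures at 36 and 12 pairs rest on an assumed 20% loss (45 x 0.8 and 15 x 0.8), and the pooled figures assume a common share across cohorts. The 81.1% rests on an assumed normal model and shows only that a continuous analysis can be more informative.

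The consequence is limited. pERK is one candidate biomarker under an exploratory objective. The committed PD review that sets the Part B dose comes before Part B (Protocol 7.2.3 and 10.9), so these pairs do not feed it, and the Part B interim review is optional. What is affected is how target engagement is read.

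**What to change.** 1. **Protocol 6.2.** State whether the 15 patients are each cohort or some other group. Replace the assumption of complete biopsies by an expected number of usable pairs, and restate the power with an exact rule for that number. For 10% versus 30%, this would be 51% at 12 pairs (4 or more). If all Part B pairs are used, it would be 95% at 45 (9 or more) or 89% at an assumed 36 (8 or more).
2. **SAP 5.10.** Name the within-patient change in pERK, on-treatment against pre-treatment, as the main PD summary with a 90% confidence interval. Use the log ratio, reported as geometric mean percent inhibition, if the assay scale allows it. Otherwise use a rank-based paired summary. Show it by cohort and across all Part B pairs taken at the same dose, state how unpaired samples are handled, and keep the proportion with at least 50% inhibition beside it.

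The cost is wording in two documents, with no extra patient, biopsy or assay. The small downside is that the pooled estimate averages over three tumour and mutation groups, so the cohort results must stand next to it.
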